In addition, the CCHMC study team will receive a Propeller Health daily report of participants that have not taken their daily controller medication in the last 7 days, have changed their asthma symptoms control level, or have experienced a 200% increase in their rescue medication use in the past 24 hrs. The study team will communicate with both the school nurse and the participant to gather more information on the severity of their asthma symptoms using the Phone Call Exacerbation Form. If the participant is experiencing severe symptoms, they will be encouraged to be urgently evaluated by the school nurse, school-based health clinic, community primary care provider, or a local urgent care or emergency department.

Study Termination. During each medical visit, the number of severe asthma exacerbations [treated with \geq 4 days of systemic steroids; \geq 2 hospitalizations for asthma; \geq 1 PICU admission, intubation or hypoxic seizure due to asthma] since the start of the study will be determined. If the participant has \geq 4 severe asthma exacerbations, study participation will be ended. The procedures for the end of study will also be followed with the recommendation of referral to the CCHMC Difficult-to-Treat Asthma Clinic.

End of study. At the end of the study, the participant and their parents/legal guardians will be given a letter which summarizes which medication the participant was prescribed at the last month of the study. The study team will make sure that the participant has 2 additional refills at the end of the study. The letter will encourage them to make an appointment and visit their primary care physician within 2 months of the study end. Information on how to make an appointment at CCHMC Asthma Center will also be provided.

9. DATA ANALYSIS/METHODS:

Study Outcomes:

The adolescent's asthma outcomes and adherence will be measured at baseline and during the monthly medical visits for a total of 6 months. Outcomes will be measured during the monthly medical visits using a computerized TreatSmart program based on the NAEPP asthma guidelines which was adapted by the CCHMC Asthma Center database team from the Inner City Asthma Coalition (Appendix B), ACT scores (Appendix C), and Propeller Health web-based inhaler cap monitoring sensor and mobile software management platform (Appendix A).

Primary Outcome:

Two-week histories of asthma symptoms measured per month (daytime symptoms, nighttime symptoms, or activity limitations) during the intervention period (from completion of the first month to study exit). The symptoms will be measured by a two-week recall of adolescent captured by the TreatSmart program.

Secondary Outcomes:

ACT score over past 4 weeks; rescue medication use (Propeller Health monitoring), oral-steroid requiring exacerbations questionnaires (2-week recall TreatSmart program); school absences (parent and subject report), adherence of controller medication (Propeller Health monitoring).

The asthma symptom burden, ACT score, exacerbation, healthcare utilization outcomes are commonly reported in both the adult and pediatric asthma literature, are endorsed by national asthma guidelines and the National Institutes of Health (NIH) asthma-outcome conference, and will also be measured.

Data Analysis

We will use descriptive statistics to characterize the sample demographics. A descriptive analysis with calculation of means, medians, and standard deviations will be performed for each continuous measure; categorical measures will be examined with percentages. We used paired t-tests to evaluate the null hypothesis that there was no change in the primary outcomes (two-week histories of daytime symptoms, nighttime symptoms, or activity limitations) while participants are blinded to data collected by the Propeller medication sensor in the first month of participation. Nonparametric methods will be used if the assumptions for paired t-tests are violated. The primary analyses will test whether the school-based interventional program improves two-week histories of asthma symptoms measured per month (daytime symptoms, nighttime symptoms, or activity limitations) during the intervention period (from completion of the first month to study exit). Linear mixed effects models with a random effect for subject assessed changes in primary asthma endpoints across the five subsequent months of enrollment (at the completion of the first month, the second month, the third month, the fourth month and the fifth month upon exit) when participants will be able to access their usage data online. Participants with one or more observations will be included in the analysis. All statistical analyses will be implemented in SAS 9.3 (SAS Institute, Cary, NC) and use a significance level of 0.05. Potential confounders identified from the literature, such as age, gender, season of enrollment, severity of asthma at baseline, smoke exposure, history of allergic disease, will be adjusted in the analyses. The REML model used for these analyses requires that any missing data are "missing at random" (MAR) to yield valid estimates. In order to account for the presence of possible non-ignorable missing data, pattern-mixture modeling will be applied for these analyses.

The secondary analyses will look at the health system utilization, rescue medication use, adherence and lost school days. Linear mixed-effect models will be used to compare the continuous outcomes such as lost school days. Generalized linear mixed effect models will be used to compare the discrete outcomes such as health system utilization, both accounting for repeated measurement over time while adjusting for confounders.

Future use

The de-identified data may be used for future research, analysis or recruitment. All reidentification codes will be destroyed.

10. FACILITIES and PERFORMANCE SITES:

External sites will be at Cincinnati Public Schools or home of the participant or the Cincinnati Children's Hospital and Medical Center CCHMC Pulmonary Division and CTRC.

11. POTENTIAL BENEFITS:

Participants will have direct benefit of being closely monitoring for their asthma and clinical care. The future benefit is to strive to develop "asthma-free schools" in neighborhoods where the incidence of asthma is especially high.

12. POTENTIAL RISKS, DISCOMFORTS, INCONVENIENCES AND PRECAUTIONS:

The risks to participants are minimal and include:

- Missed school classroom time to participate in the school study visits: Efforts will be made to minimize testing during class time such as conducting them over the lunch hour, during study halls or non-core classes, or afterschool.
- Asthma Questionnaires: There is a slight inconvenience to the family in the time required to answer questionnaires.
- Confidentiality: There is a slight risk of unintentional release of PHI.

Concerns about Access Adult Websites and Apps on Cell Phones:

Participants will be provided with a cellular phone for use over a 6 month period. During the consenting and assenting process, participants will be asked to use the cellphone "as they normally would use any smartphone that has internet access". We have gone to great lengths to make the cell phones provided easy to use and compelling in terms of incentives and features so that participant will use the cell phone provided as opposed to other cell phones they likely have. However, for this endeavor to be successful, participants must feel confident that their phone activity--how they normally use the phone--will not be met with repercussion or reprimand.

We considered only installing the Propeller Health software apps and severely restricting the internet website allowed to be accessed on the study cell phones. However, this would create an "unnatural" cell phone use environment for those participants that had not previously been exposed to filtering and would cause them to not use the study cell phone as their main device they carry with them. Therefore, we have consulted closely with CCHMC's IT and Office of Research Compliance to adequately design the following

procedures for informing parent/guardians of their options, and adhering to parent/guardians' wishes, while not compromising the integrity of the study. Hence, the smart phones will be loaded with a security software program Air Watch and include a basic package of social media apps that middle-schoolers and adolescents frequently use. We will list out for the parent/guardians that apps are installed on the phone and brief descriptions of the risks and benefits and they will be told this is similar to their teen's current cell phone. After being informed, parent/guardians and participants will then be given an instruction sheet (See Appendix B) on how to use the cell phone. Within this instruction sheet there will be instructions on how to add apps by using the family's apple ID account or removing apps from the cell phone if the participants or parent/guardian desire. However, CCHMC IT will be alerted if the Propeller Health app is removed from the phone. The Air Watch security software enforces specific security measures, such as passcode and encryption. The study team working with the CCHMC IT department will be able to erase all content in the event of a lost/stolen device. The Air Watch security software does not monitor the participants' usage or personal information. Internet access on the smartphone is being restricted with Apple's built in Adult Content Filter for the Safari web browser. This content filter does its best to block websites with inappropriate content. The Internet content filter can identify, with a high degree of accuracy, whether a Web page is safe or not by examining various properties of the website including text and structure. The content filter is being managed by the Air Watch security software and cannot be removed.

13. RISK/BENEFIT ANALYSIS:

This study is minimal risk with direct benefit to the participants. It builds on the CCHMC-CPS-CHD existing asthma QI program to improve asthma care and it provides more comprehensive asthma management and monitoring than many of these participants currently receive.

14. DATA SAFETY & MONITORING:

DSMP:

The Data Safety and Monitoring Plan (DSMP) will consist of a Steering Committee made up of [name] and key study personnel. The committee will meet annually to review adverse events and to provide oversight and coordination of project management, research administration, publications and data sharing, and integration of all resources needed for the project.

Adverse Events:

Events that are unexpected and related to the conduct of medical or adherence visits or asthma symptoms will be reported promptly to the IRB according to IRB policy. Serious, life threatening events that are related to study related procedures will be reported to the IRB within 48 business hours. All other adverse events that happen in the course of study procedures as well as minor deviations from protocol will be reported in table form at the next continuing review.

Any untoward or unfavorable medical occurrence associated with the subject's participation in the research, whether or not considered related to the subject's participation in the research (modified from the definition of adverse events in the 1996 International Conference on Harmonization E-6 Guidelines for Good Clinical Practice) (from OHRP "Guidance on Reviewing and Reporting Unanticipated Problems Involving

Risks to Subjects or Others and Adverse Events (1/15/07)"
<http://www.hhs.gov/ohrp/policy/advevntguid.html#Q2>).

For this study, the occurrence of wheezing episodes and the development of allergic rhinitis are anticipated events and will be recorded as expected AEs. This information will also be collected on other study forms. Fluctuations in the status of pre-existing atopic dermatitis, a process that is expected to wax and wane in severity, will not be recorded as an AE unless, in the opinion of the site investigator, the degree of deterioration is unexpected for the participant.

An adverse event or suspected adverse reaction is considered "unexpected" if it is not listed is not consistent with the risk information described in the general investigational plan.

An adverse event or suspected adverse reaction is considered "serious" if, in the view of either the investigator, it results in any of the following outcomes (21 CFR 312.32(a)):

1. Death.
2. A life-threatening event: An AE or SAR is considered "life-threatening" if, in the view of either the investigator its occurrence places the subject at immediate risk of death. It does not include an AE or SAR that, had it occurred in a more severe form, might have caused death.
3. Inpatient hospitalization or prolongation of existing hospitalization.
4. Persistent or significant incapacity or substantial disruption of the ability to conduct normal life functions.
5. Congenital anomaly or birth defect.
6. Important medical events that may not result in death, be life threatening, or require hospitalization may be considered serious when, based upon appropriate medical judgment, they may jeopardize the subject and may require medical or surgical intervention to prevent one of the outcomes listed above.

Wheezing episodes and exacerbations of asthma are anticipated events in the population under study even when receiving standard of care therapy. A hospitalization for wheezing or asthma will not be recorded as an SAE unless it is considered a serious and unexpected suspected adverse reaction SUSAR (9.3.2). All other hospitalizations will be recorded in the case reporting forms.

Review with family of possible adverse events will be done at medical visits and follow-up phone calls by the research coordinator if adverse events occur, will be documented. Adverse events will be recorded on an Adverse Event Reporting Form and will be reviewed at the meeting of the Steering committee.

If a parent/guardian response or complaint is not an expected adverse event (see section 4) or if the adverse event presents with greater than expected severity, the adverse event will be brought to the Investigator's attention in a timely manner for evaluation. The reviewing investigator will determine if the event is a Reportable Event as defined below.

Definition of Reportable Events

Reportable events must fall into one of the categories below:

1. Adverse event that is BOTH unexpected AND related or possibly related to participation in the research. This is regardless of whether internal or external site or seriousness.

2. An event that requires a change to the protocol or informed consent.
3. Information that indicates a change to the risks or potential benefits of the research.
4. Breach of confidentiality.
5. Change in labeling or withdrawal from marketing for safety reasons of a device used in research protocol.
6. Change to protocol made without prior IRB review to eliminate an apparent immediate hazard to a research participant.
7. Protocol violation that harmed a participant or others or indicates that participants or others are at increased risk of harm.
8. Incarceration of a participant in a protocol not approved to enroll prisoners.
9. Complaint of a participant that indicates unexpected risks or cannot be resolved by the research team.
10. Other unanticipated problem posing potential risk to participants or others comparable to the events listed above that are BOTH unexpected/unanticipated AND have a reasonable possibility of relatedness to the research.
11. INVESTIGATIONAL DEVICES: Unanticipated adverse device effect, deviation from the protocol to protect the life of a subject in an emergency, or any use of the without obtaining informed consent.

15. PRIVACY and CONFIDENTIALITY:

Confidentiality of Participant Data:

Precautions to protect the privacy of participant data include:

- Participants will be given a study ID that does not include any personal identifiers for study records and questionnaire data stored outside of CCHMC EPIC.
- A study ID not related to any PHI will be used in the study database.
- All electronic research data will be reviewed by the statisticians without PHI.
- The ID code and the research records will be maintained in a secured location and/or in password protected databases.
- Summary of the school-based medical and adherence visits will be documented in the CCHMC EPIC medical record which can be accessed by school nurses and community primary care physicians who have been granted read-only access by CCHMC.
- Propeller Health data is stored on a HIPPA compliant server and has been approved by CCHMC IT and equipment committee.
- TreatSmart program and data are located on a CCHMC secure server.

To minimize risk, the source document will be kept in the research record and stored in a secure location. Data will be entered into password protected databases with participants identified with a study number that contains no PHI. To minimize the inconvenience, we are limiting administration of the baseline questionnaires to the baseline visit. The adherence questionnaire will be given at the first and last medical visit. The TreatSmart program will take 10 minutes to complete.

16. COST OF PARTICIPATION:

There is no cost to participants for the phone, data plan, Propeller caps or for medical care received as part of the study visits.

The cost of prescriptions and sick visits will be the responsibility of the subject and their insurance.

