There will be Post-Visit Surveys for subjects, parents and nurses that will be done periodically throughout the study. Survey participants will receive e-mails from the study team through RedCap for the surveys to be completed online directly into RedCap. The purpose of the surveys is feedback for effectiveness/satisfaction with the telehealth and propeller device. All participants who complete their response to the Post-Visit Surveys (subject, parent, school nurses) will receive \$10 added to their ClinCard. Nurses may be approached and asked follow-up questions regarding their perceptions of the study (see appendix X).

Visit 1- Baseline Medical Visit: This visit will be conducted in one of the following locations: the home, CCHMC, school nurse office or school-based health clinic, whichever location is more convenient for the family.

The coordinator will consent the parent/legal guardian(s) and obtain assent from the child/adolescent. Baseline questionnaires will be completed by a parent/guardian and participant and the study visits and procedures will be explained. A smart phone prepared by the CCHMC IT team with a data plan will be provided to the participant.

Basic asthma education will be provided. The study coordinator will conduct this visit. The participant will complete an Asthma Control Test (ACT) and the study coordinator will assist the participant to complete the TreatSmart program on a CCHMC secured laptop. The TreatSmart software web-based program, developed at CCHMC and hosted on a CCHMC secure server, will be used to determine the participant's symptom burden, health care utilization, systemic corticosteroid use, and current medication use to determine the level of asthma severity/control the participant has. The program also makes an initial treatment recommendation based on the National Asthma Education and Prevention Program (NAEPP asthma guidelines) if the participant's asthma meets the definition of persistent asthma and if their treatment dose should remain the same or be changed based on their level of control. This program will also produce a visit summary and asthma action plan. The TreatSmart program takes approximately 10 minutes to complete.

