After the TreatSmart program is completed, the study coordinator would connect with a CCHMC Asthma Center asthma pulmonary or allergy specialist investigator ([name], [name], [name], [name]) to conduct a telehealth visit using CCHMC-provider Jabber software on the laptop (similar to Skype but HIPAA compliant) to perform a physical exam, review the TreatSmart program visit summary and treatment recommendations and make a final decision of the level of asthma control and asthma medication needed. The laptop-based Jabber software has been implemented successfully in other clinical visits through the CCHMC Telehealth Program. The visit summary, asthma medication recommendation and asthma action plan from the medical visit will be documented in the CCHMC medical record as a telehealth visit and physically given, mailed or faxed to the participant, family, school nurse and primary care provider by the study team. Through our QI work, the school nurses and community primary care providers have read-only access of EPIC and can access these medical records after this visit.

If no change in current asthma medication required: The study coordinator will place the Propeller Health monitoring caps on the participant's current inhalers, register the Propeller Health inhaler monitoring caps with Propeller Health, and review how to take the medication with the participant. Prescriptions for asthma medications and inhaler spacers will be written by the study physician and sent to a delivery pharmacy as required.

If new asthma medication required: Prescriptions for asthma medications and inhaler spacers will be written by the study physician and sent to a delivery pharmacy if required. The medications will be delivered to a central location; either the school nurse office, school-based clinic or CCHMC depending on the school and family's preference. The study coordinator will place the Propeller Health monitoring caps on the inhalers and arrange a time for the participant to pick up their medications at school or deliver them to their house, sync the inhaler caps with their smartphone app, and review how to take the medication with the participant. Prescriptions for asthma medications and inhaler spacers will be written by the study physician and sent to a delivery pharmacy as required.

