Visit 2 - Visit 7: These visits will be conducted in one of the following locations: school nurse office, school conference room or school-based health clinic. These visits will occur at school or CCHMC over the lunch hour, during a study hall or non-core class, or afterschool. The study visits may be combined with school clinic visits with routine clinic care including vital signs and asthma assessments delivered by the school nurse or their assigned nursing students. Parent/guardian participation is not required for these visits. At visit 2, the coordinator will sync the Propeller app on the participant's cell phone and

the Propeller Health web platform with the inhaler caps so they and their family can see their inhaler use data for the rest of the study.

Each visit, the participants will be encouraged to use only the inhalers with the caps on them and given instructions to call the study team for replacements if they lose their medications.

After the baseline visit, 6 monthly medical Study Visits will be scheduled to assess the participant's level of asthma control and adjust the asthma medications as needed by the TreatSmart program using the same procedures as outlined above in the baseline medical visit.

Procedures done at these visits include:

- Questionnaires, ACT, TreatSmart
- Review of adherence from Propeller cap data
- Telehealth visit and medical evaluation
- Review of prescriptions and adjustment as needed
- Post-visit REDCap survey link will be emailed to the parent after medical visits 1 and 6 to solicit feedback on the telehealth visit to elicit feedback on participating in the study and use of the Propeller and telehealth technology.
- Post-visit REDCap survey link will be emailed to the child after the V2 and V6 medical visits and the first adherence visit to solicit feedback on the telehealth visit to elicit feedback on participating in the study and use of the Propeller and telehealth technology. The content of the survey is similar to the parent survey, The parent will be informed at the time they take the survey that a similar survey will be sent to their child and to contact the study team if they have questions or concerns about the survey content.

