Based on the community primary care provider (PCP) focus group feedback, the primary care providers will have 2 business days to communicate back to the study team with any concerns about the proposed medication plan and the study physicians will reach out and come to a consensus regarding the asthma medication and new prescriptions will be provided based on the consensus plan.

If the participant does not have a primary care provider, we will follow the current standard of practice at school where the school nurse provides the family a list of practices close to the school. If contact is made with a primary care physician, we will include them in the study as outlined above.

Propeller Health Inhaler monitoring and Web-based Platform During the Study Visit 1:

Propeller Health, a web-based inhaler cap monitoring sensor and mobile software management platform will be used to monitor how frequently the participant uses their inhaled asthma medication (Appendix A). The monitoring cap will be placed on both the controller and rescue inhalers by the study team and they will be registered with Propeller Health. The inhaler use will be recorded on the web platform. Starting at Study Visit 2, a mobile-based app program will be available for both android and IOS platforms and will allows the participant and family to interact directly with the platform. This is a FDA approved, HIPAA compliant device that has been demonstrated to improve asthma outcomes and adherence measures. This equipment has been approved by the CCHMC Equipment committee pending approval by the IRB. A contract and data use agreement is currently being reviewed by the CCHMC legal and business offices.

During the first month of the study, we will establish the participant's baseline adherence to daily asthma controller medication and need for rescue short-acting beta-agonist. Thus, the study team, school nurse, participant and family will be blinded to this baseline data collection.

Propeller Health Inhaler monitoring and Web-based Platform during Study Visits 2-6:

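### The new-medication path at Visit 1 syncs the caps to the participant's app, although the protocol elsewhere withholds the app until Visit 2 and blinds the first month

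*Combined protocol and SAP*

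**What the plan says.** Section 8, Visit 1 (Baseline Medical Visit), gives two paths according to the outcome of the telehealth assessment.

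- **No change in medication.** The coordinator puts the monitoring caps on the current inhalers and is to "register the Propeller Health inhaler monitoring caps with Propeller Health, and review how to take the medication with the participant". No app is mentioned.
- **New medication.** The coordinator puts caps on the newly delivered inhalers, arranges pick-up or home delivery, and is to "sync the inhaler caps with their smartphone app, and review how to take the medication with the participant". No registration step is named.

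The phone is handed over at the same visit: "A smart phone prepared by the CCHMC IT team with a data plan will be provided to the participant".

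The rest of the protocol places participant access later.

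- Section 8, Visit 2 - Visit 7: "At visit 2, the coordinator will sync the Propeller app on the participant's cell phone", together with the web platform, and the stated reason is "so they and their family can see their inhaler use data for the rest of the study".
- Section 8, Propeller monitoring at Study Visit 1: caps are "placed on both the controller and rescue inhalers by the study team and they will be registered with Propeller Health". On the app: "Starting at Study Visit 2, a mobile-based app program will be available for both android and IOS platforms". The same subsection uses the first month to establish baseline controller adherence and rescue use, and blinds the study team, school nurse, participant and family to those data.
- Section 8, Propeller monitoring at Study Visits 2-6: the platform is switched on, and participant and parent receive access, at the second visit.
- Section 9, Data Analysis: the first month is described as blinded to sensor data, and the following five months as the period with online access.

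**The concern.** A coordinator who follows the new-medication paragraph literally would connect the caps to the participant's app during the month in which participant and family are meant not to see their use. The protocol's own explanation of the Visit 2 sync is that it lets them see it.

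What is at stake is the sensor baseline. The first month is the only stretch of monitoring planned without feedback, and it is where controller adherence and rescue use are to be established. The protocol itself credits the device with improving adherence, so on its own premise early access could change what is being measured. Any early access would fall only on participants whose treatment changed at Visit 1, who are not a random subset, and the design has no control group against which a distorted baseline would show up.

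The loss of blinding is an inference. The protocol does not say that the app would be usable, or would display data, before Visit 2 on this path.

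**Working it through.** The plan gives no figure to reproduce here. The check sets the instructions side by side and then counts what they affect.

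**Timing of cap and app steps**

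| Place | Caps registered | App synced or available | Participant can see data |
|---|---|---|---|
| Section 8, Visit 1, no change | Visit 1 | not mentioned | not mentioned |
| Section 8, Visit 1, new medication | not mentioned | when the new inhalers are handed over | not mentioned |
| Section 8, Visit 2 - Visit 7 | not mentioned | Visit 2 | from Visit 2, as the purpose of the sync |
| Section 8, Propeller at Visit 1 | yes, all caps | from Visit 2 | blinded in the first month |
| Section 8, Propeller at Visits 2-6 | not mentioned | platform on at the second visit | from the second visit |
| Section 9, Data Analysis | not mentioned | not mentioned | blinded in the first month, then access |

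**Reading the table**

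1. The new-medication row is the only one that puts an app step before Visit 2. It conflicts directly with the two rows that time the sync and the app's availability.
2. Its conflict with the blinding statements depends on whether a synced app shows data. The Visit 2 text links the sync to seeing the data, and nothing under Visit 1 says the display is disabled.
3. No text exempts the new-medication path, and nothing defers hand-over of the new inhalers to Visit 2. The participant already has the study phone.
4. Monthly visits after baseline adjust medication "using the same procedures as outlined above in the baseline medical visit". The clause fits naturally there, so a missing limit to Visit 2 onward is a likely origin, though the text does not confirm this.

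**Counts the documents support**

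- Visit 1 paths with the sync clause: 1 of 2.
- Intervals planned without feedback: 6 months of participation − 5 months with access (Section 9) = 1, so 1 of 6.
- Secondary outcomes listed in Section 9: ACT score, rescue medication use, exacerbations requiring oral steroids, school absences, controller adherence = 5. Those measured by the sensor: rescue use and controller adherence = 2, so 2 of 5. Both are named again in the secondary analyses.
- Participants on the new-medication path: not stated, so anywhere from 0 to 30 of the planned 30.

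The documents give neither the time from Visit 1 to pick-up nor the effect of app access on use. No bias or loss of power can therefore be computed.

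**The case against.** The strongest reply is that this is a stray clause outweighed by the dedicated text. Three parts of Section 8 and the analysis section state the Visit 2 start or the blinded month explicitly, and none varies by medication path. The schedule table also has a separate row for loading the Propeller system on the phone. Its columns are displaced in the text available for this review, so the exact visit cannot be read from it, but its order suggests loading after the phone and caps are dispensed. There may be no app to sync in the first month. Syncing may also be only data transfer: the sample dashboard in Appendix A shows a last-sync date for each inhaler, and first-month use has to reach the web platform somehow. Finally, Section 9 specifies no contrast of first-month adherence or rescue use with later months, so no particular estimate can be named as biased.

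Much of this stands. It makes loss of blinding a possibility rather than a certainty, and it rules out any claim about size. It does not remove the conflict. Pairing without display is not stated under Visit 1, and even on that reading the app timing still disagrees with the Visit 2 text and the availability statement. The schedule row, so far as it can be used, is one more place out of line with the clause. The missing registration step carries little weight, because the Propeller subsection registers all caps.

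**Conclusion.** The concern holds, and the Visit 1 clause is wrong as written. The contradiction over when the app is synced is plain in the text. The consequence is conditional: if the clause is followed and the synced app displays data, first-month controller adherence and rescue use for participants given new medication at Visit 1 would not be the blinded baseline the protocol describes. The effect is zero if the clause is not followed or the display stays off until Visit 2.

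No effect is claimed on the primary symptom analyses, because both the first-month test and the mixed model use symptoms recalled in TreatSmart rather than sensor data. The point should be corrected. Confidence is medium, because the practical consequence rests on app behaviour that the protocol does not describe.

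**What to change.** Reconcile the new-medication paragraph under Visit 1 with the Visit 2 - Visit 7 text, the two Propeller subsections of Section 8 and the Data Analysis text of Section 9. Either of two wordings would do.

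1. Have both Visit 1 paths place and register the caps without participant app access, and limit the app-sync clause to Visit 2 onward. The clause then still covers new inhalers issued at later visits.
2. If pairing before Visit 2 is technically needed, state that the app display stays off for participant and family until Visit 2.

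Optionally, record the date of first app access for each participant, so that any early access can be reported as a deviation and those participants identified in the adherence and rescue-use summaries.

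The cost is one qualifying clause and, if wanted, one date field. The change concerns device set-up only and leaves treatment rules untouched.
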